6.2.4. Sensitivity Analysis of the Primary Endpoint

Sensitivity analyses of the primary efficacy endpoint will be performed.

6.2.4.1. Per-protocol Analyses

To evaluate the impact of study conduct on the primary analysis, the proportion of subjects who achieve ACR20 at Week 12 will be analyzed based on the PP Analysis Set as defined in Section 3.1.3 using the logistic regression analysis with NRI for the comparisons of each filgotinib group versus the placebo group. The p-value from the logistic regression model will be provided. The 2-sided 95% CI of the ACR20 response rate at Week 12 based on normal approximation with the sample variance for each treatment group will be provided. In addition, the non-stratified ACR20 response rate difference along with its 95% CI calculated based on the normal approximation with the pooled sample variance will also be provided.

6.2.4.2. Missing Data Imputation Analyses

To evaluate the impact of missing data on the ACR20 response rate at Week 12, the following missing value imputation methods will be used:

- The analysis specified in Section 6.2.3 will be performed by using OC and LOCF methods as described in Section 6.1.
- Multiple imputation (MI): The MI procedure replaces each missing binary ACR20 value with a set of plausible values that represent the uncertainty about the right value to impute. Twenty imputed datasets will be generated based on logistic regression models with starting seed 12345. These multiple imputed data sets are then analyzed by using the same method for the primary analysis for complete data as specified in Section 6.2.3. The results from each set of imputed data sets will then be combined using Rubin's rule {Rubin 1987}. The stratification factors will be included in the imputation model as covariates and data at post-baseline visits up to the time point of interest will be included in the longitudinal model.

- Tipping point analysis: To assess the robustness of analysis results under MNAR (missing not at random) assumption, a delta-adjusting pattern-mixture approach for tipping point analysis {Ratitch 2013} will be conducted for the primary efficacy endpoint. The impact from missing data on the comparisons in proportion of subjects achieving ACR20 at Week 12 between filgotinib groups and placebo control group will be examined, by adjusting for stratification factors. The proposed method will perform a series of analyses with a range of different values of the shift parameter δ applied to the imputed datasets at which the conclusion about the statistical significance of the estimated treatment effect will be altered. Specifically, a tipping point analysis is characterized by a pair of sequences (one sequence associated with missing data in the placebo group and the other associated with missing data in the filgotinib group). In the first step for both sequences, the missing data in both treatment groups are imputed under the MAR assumption. For each subsequent step of the placebo sequence, the missing data is imputed assuming the missing data is incrementally more favorable than in the previous step of that sequence. Similarly, for each subsequent step of the active sequence, the missing data is imputed assuming the missing data is incrementally less favorable than in the previous step of that sequence. Appendix 6 provides sample SAS model statements for the tipping point analysis with starting seed. Each δ value is classified as either ‘altering the study’s conclusion’ or tips, ‘keeping the study’s conclusion unchanged’. The tipping points that alter the statistical conclusion will be provided. For each δ value, 20 imputed data sets will be generated. The same analysis method for the primary analysis as specified in Section 6.2.3 will be applied when analyzing adjusted data generated under the different δ values.

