6.3.3.2. Missing Data Imputation Analyses

The following imputation methods will be explored:

- Change from Baseline in HAQ-DI score at Week 12
 - 1) MI: All subjects with baseline measurement will be included. The MI procedure replaces each missing value with a set of plausible values that represent the uncertainty about the right value to impute. Twenty imputed datasets will be generated based on linear regression models on observed HAQ-DI scores with starting seeds 123 and 465. These 20 imputed data sets are then analyzed by using the analysis method specified in Section 6.3.2 for complete data. The results from each imputed data set will then be combined using Rubin's rule {Rubin 1987}. Stratification factors and baseline values will be included in the imputation model as covariates, and data at baseline and all post-baseline visits up to the time point of interest visit will be included in the longitudinal model.
 - 2) Tipping point analysis: All subjects with baseline measurement will be included. To assess the robustness of analysis results for change from Baseline in HAQ-DI at Week 12 under MNAR assumption, a set of the shift parameters that adjust the imputed values will be examined {Yuan 2014}. The shift parameter that alters the study conclusion for the hypothesis testing for change from Baseline in HAQ-DI at Week 12 under the MAR assumption will be reported as the tipping point and provided. The tipping point analysis will be conducted by iteratively assigning plausible outcomes to missing values for subjects in different treatment group independently until the conclusion is reversed (eg, analyses are no longer statistically significant). Appendix 7 provides sample SAS model statements for the tipping point analysis with starting seeds. The same analysis method for the primary analysis as specified in Section 6.3.2 will be applied when analyzing adjusted data generated under each plausible shift parameter.
- Proportion of subjects who achieve DAS28(CRP) < 2.6 at Week 12
 - 1) The analysis using the same logistic regression model specified in Section 6.3.2 will be performed by using OC and LOCF methods as described in Section 6.1.

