 - 2) MI: All subjects with baseline measurement will be included. The MI procedure replaces each missing composite DAS28(CRP) value with a set of plausible values that represent the uncertainty about the right value to impute. Baseline value and stratification factors will be included in the imputation model as covariates, and data at baseline and post-baseline visits up to the time point of interest will be included in the longitudinal model. The multiple imputed datasets will be generated. These multiple imputed data sets are then used to identify subjects with DAS28(CRP) < 2.6 at Week 12, and analyzed by using the analysis method specified in Section 6.3.2 for complete data. The results from each set of imputed data sets will then be combined using Rubin's rule {Rubin 1987}.
 - 3) Tipping point analysis: Similar modified tipping point method as described in Section 6.2.4.2 will be applied to DAS28(CRP) < 2.6 response rate at Week 12.

- Change from Baseline in mTSS at Week 24
 - 1) MI: Similar MI procedure used for analyzing the change from Baseline in HAQ-DI score at Week 12 will be performed.
 - 2) Tipping point analysis: Similar tipping point analysis method used for analyzing the change from Baseline in HAQ-DI score at Week 12 will be performed.
- Non-inferiority analysis of the proportion of subjects who achieve $\text{DAS28(CRP)} \leq 3.2$ or $\text{DAS28(CRP)} < 2.6$ at Week 12
 - 1) The non-inferiority analysis using the same test specified in Section 6.3.2 will be performed by using OC and LOCF methods as described in Section 6.1.
 - 2) MI: Similar MI procedure used for superiority test of the proportion of subjects who achieve $\text{DAS28(CRP)} < 2.6$ at Week 12 will be performed. The multiple imputed data sets will be analyzed by using the non-inferiority analysis specified in Section 6.3.2 for complete data. The results from each set of imputed data sets will then be combined.
 - 3) Tipping point analysis: Similar modified tipping point method as described in Section 6.2.4.2 will be applied to $\text{DAS28(CRP)} \leq 3.2$ or $\text{DAS28(CRP)} < 2.6$ response rate at Week 12. The non-inferiority analysis specified in Section 6.3.2 will be applied when analyzing adjusted data generated under the different δ values.
- Change from Baseline in SF-36 PCS at Week 12
 - 1) MI: Similar MI procedure used for analyzing the change from Baseline in HAQ-DI score at Week 12 will be performed.

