Appendix 7. SAS Programming for Tipping Point Analysis for Continuous Endpoint

The following **%tp_conti** macro generates multiple imputed data sets and a set of the shift parameters that adjust the imputed values will be examined.

```

/*****
/*--- Modified Tipping Point Analysis from Yuan's method ---*/
/*---
/*--- Generate imputed data set for specified shift parameters ---*/
/*--- data= input data set ---*/
/*--- smin= min shift parameter for active drug ---*/
/*--- smax= max shift parameter for active drug ---*/
/*--- sinc= increment of the shift parameter for active drug ---*/
/*--- pmin= min shift parameter for placebo drug ---*/
/*--- pmax= max shift parameter for placebo drug ---*/
/*--- pinc= increment of the shift parameter for placebo drug ---*/
/*--- trt= treatment group indicator (eg, 1= filgotinib 200 mg) ---*/
/*--- out= output imputed data set ---*/
*****/

```

```

%macro tp_conti( data=, smin=, smax=, sinc=, pmin=, pmax=, pinc=, trt=, out=);
  data &out;
  set _null_;
  run;

```

```

  %let ncase_pbo = %sysevalf( (&pmax-&pmin)/&pinc, ceil );

```

```

  %do pc=0 %to &ncase_pbo;

```

```

    %let pj= %sysevalf( &pmin + &pc * &pinc);

```

```

    /*----- # of shift values -----*/
    %let ncase= %sysevalf( (&smax-&smin)/&sinc, ceil );

```

```

    /*----- Imputed data for each shift -----*/
    %do jc=0 %to &ncase;

```

```

      %let sj= %sysevalf( &smin + &jc * &sinc);

```

```

      proc mi data=&data out=all_mono nimpute=20 seed=123;
        var v_1 v_2 v_3 v_4 v_5 v_6 v_7 v_8 v_9;
        mcmc chain=multiple impute=monotone;
      run;

```

```

      proc sort data=all_mono; by _Imputation_ trt01pn; run;

```

```

      proc mi data=all_mono out=outmi seed=465 nimpute=1;
        by _Imputation_ ;
        var trt01pn strat1V strat2V strat3V v_1 v_2 v_3 v_4 v_5 v_6 v_7 v_8 v_9;
        class trt01pn strat1V strat2V strat3V;
        monotone regression;
        mnar adjust( v_5 / adjustobs=(trt01pn="&trt") shift=&sj)
              adjust( v_5 / adjustobs=(trt01pn='3') shift= &pj);

```

```
run;

data outmi;
    set outmi;
    Shift_Trt= &sj;
    Shift_Pbo= &pj;
run;

data &out;
    set &out outmi;
run;
%end;
%mend tp_conti;
```

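### Appendix 7 leaves some missing Week 12 HAQ-DI values out of the tipping-point shift, and the ACR20 and DAS28(CRP) imputation models do not name treatment

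*SAP*

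**What the plan says.** **Multiple imputation (MI), text.**
- ACR20 (SAP 6.2.4.2): "The stratification factors will be included in the imputation model as covariates and data at post-baseline visits up to the time point of interest". Neither treatment nor a baseline value is named, and no MI code is printed.
- HAQ-DI (SAP 6.3.3.2): "Stratification factors and baseline values will be included in the imputation model as covariates, and data at baseline and all post-baseline visits", with the visits again ending at the target visit. The method is "linear regression models on observed HAQ-DI scores with starting seeds 123 and 465". mTSS, SF-36 PCS and FACIT-Fatigue follow a similar procedure.
- DAS28(CRP) (SAP 6.3.3.2): "Baseline value and stratification factors will be included in the imputation model as covariates, and data at baseline and post-baseline visits", ending at the target visit. No MI code is printed. The same procedure is reused for the non-inferiority tests.

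**Tipping point.** SAP 6.3.3.2 says that outcomes are assigned to missing HAQ-DI values independently by treatment group, and points to Appendix 7 for sample code. mTSS, SF-36 PCS and FACIT-Fatigue use a similar method.
- Appendix 7, step 1: "var v_1 v_2 v_3 v_4 v_5 v_6 v_7 v_8 v_9" with "mcmc chain=multiple impute=monotone". There is no treatment variable, no stratum and no BY treatment.
- Appendix 7, step 2: monotone regression on `trt01pn`, three stratum variables and v_1 to v_9. The MNAR shift is applied to v_5 in the selected active arm and in the placebo arm.
- Appendix 6 (binary endpoints): one step with `trt01pn`, the strata and ACR20, and no MCMC.

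**The concern.** A tipping-point analysis asks how bad the missing values would have to be to overturn a result. If some of them cannot be moved, a larger nominal shift is needed and the result looks sturdier than it is. The printed code has that property for any subject with a gap at Week 12 and a later visit. It also conflicts with the text of SAP 6.3.3.2, which stops at the target visit and treats the arms separately.

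The MI analyses are a stated check on non-responder imputation and on the MMRM. An imputation model without treatment gives missing values in every arm the same expected outcome, given the covariates, and so pulls the arms together. For ACR20 and DAS28(CRP) the text is the only MI specification, and it does not list treatment.

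**Working it through.** **1. The plan's own figures.** No stated number is in dispute. The design inputs in SAP 1.3 reproduce: n per arm = 2 × (1.960 + 1.282)² × (1.85/0.4)² ≈ 449.5, rounded up to 450, with power 0.9003 at 450. The ACR20 rates of 45% and 65% are used in step 6.

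**2. Which visit is v_5.** The code has no labels. SAP Table 3-1 runs Baseline, Weeks 2, 4, 8, 12, 14, 16, 20, 24, which is nine visits. So v_5 is Week 12 and v_6 to v_9 are Weeks 14 to 24. If v_1 were Week 2 instead, Week 12 would be v_4 and no Week 12 value would be shifted at all.

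**3. Tracing the code.**

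| Pattern | Step 1 | Step 2 |
|---|---|---|
| Week 12 and all later visits missing | left missing | imputed with treatment and strata, then shifted |
| Week 12 missing, a later visit observed | filled from pooled arms, using later visits | no longer missing, so not shifted |

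SAP 6.1 foresees the second pattern: it sets a rule for subjects who missed Weeks 12 and 14 and are judged at Week 16. That section also applies MI and tipping point to both estimands. Under the treatment-policy data, v_6 to v_9 can therefore include values recorded on standard of care after Week 14.

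**4. Effect on the tipping shift.** Let m be the fraction of an arm missing at Week 12, f the intermittent share of those, δ the shift, and D the movement in the arm mean that overturns the result.
- All missing values shifted: the mean moves by mδ, so δ = D/m.
- Code as printed: the mean moves by m(1−f)δ, so δ = D/[m(1−f)].
- Ratio: 1/(1−f); m cancels.

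| f (assumed) | 10% | 25% | 50% | 75% |
|---|---|---|---|---|
| Inflation | 1.11 | 1.33 | 2.0 | 4.0 |

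**5. Simulation of the two steps.** Assumptions: arms of 450/450/300/450, effect 0.30 SD, 10% missing at Week 12, adjacent-visit correlation 0.8, 20 imputations, six replicates, shifts in steps of 0.25 SD. Raising the shift from 0 to 2.0 SD moved the intermittent Week 12 values by exactly 0. When every missing value was shifted with treatment in the model, the tipping shift was 0.75 to 2.25 SD at each f. With the printed procedure it was 0.75 to 2.5 SD at f = 10%, 0.75 to 3.0 at 25% and 1.0 to 5.0 at 50%. Six replicates show direction, not precise size.

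**6. Treatment not in the ACR20 model.** In the worst case earlier visits carry no information. With equal missing fraction m per arm, imputed values share one mean and the difference becomes (1−m) × (0.65 − 0.45).

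| m (assumed) | 5% | 10% | 15% | 20% |
|---|---|---|---|---|
| Difference | 0.19 | 0.18 | 0.17 | 0.16 |

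With treatment in the model it stays at 0.20. When earlier visits are informative the loss is smaller. At an assumed latent adjacent-visit correlation of 0.7 to 0.9 the difference shrinks by about 1–3%, 2–6% and 4–13% at 5%, 10% and 20% missing.

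**The case against.** Much can be said for the plan.

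- **The primary endpoint.** A reader might infer that the ACR20 tipping point is understressed too. It is not: Appendix 6 has treatment, a single outcome and no MCMC step, so every missing ACR20 value in a shifted arm is shifted. The DAS28(CRP) tipping points are referred to that method as well.
- **HAQ-DI imputation.** A reader might infer that it ignores treatment throughout. The seeds in SAP 6.3.3.2 are those of the two Appendix 7 calls, and the second call includes treatment. Dropouts are therefore handled properly; only intermittent gaps are not.
- **The lists may not be exhaustive.** Nothing excludes treatment, and both printed macros use it. For ACR20 and DAS28(CRP) this is an omission to close, not a proven exclusion.
- **Pooled filling is minor.** In an illustrative calculation it turned a HAQ-DI effect of 0.299 into 0.277 for the gap values. If 3% of subjects skip Week 12 (assumed), the overall difference changes by 0.03 × 0.022 ≈ 0.0007. The missing shift is what matters.
- **Sample code.** Nine variables cannot fit mTSS (four analysis visits) or SF-36 and FACIT-Fatigue (six), so the code must be adapted. For those endpoints the defect recurs only if the adapted list runs past the target visit.
- **Gaps as missing at random.** Shifting only dropouts is defensible, but the SAP does not say this is intended.

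These points narrow the concern. They do not remove the conflict between Appendix 7 and SAP 6.3.3.2, or the silence on treatment in the two MI lists that have no code.

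**Conclusion.** The concern holds in limited form. Run as printed, Appendix 7 imputes intermittent Week 12 HAQ-DI gaps without treatment and never shifts them, which inflates the reported tipping shift by about 1/(1−f). This rests on v_5 being Week 12, which is inferred, and on f, which the documents do not give. The inflation is small if such gaps are rare (1.11 at 10%) and material if they are common (2.0 at 50%). No particular share can be claimed from the documents.

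The ACR20 and DAS28(CRP) MI lists, followed literally, shrink the arm difference by at most about the missing fraction. A reader might take that limit as the expected bias; it is approached only when earlier visits say little about Week 12. For superiority the direction is conservative.

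A reader might also infer that the trial's main results are at risk. They are not: the non-responder and MMRM primary analyses are untouched, and ACR20 also has observed-case, LOCF and per-protocol checks.

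**What to change.** - In SAP 6.2.4.2 and in the HAQ-DI and DAS28(CRP) paragraphs of 6.3.3.2, name treatment in the imputation model, or state that imputation is done by arm.
- In Appendix 7, step 1, sort by `trt01pn` and add `BY trt01pn`.
- End the variable list in both steps at the target visit: v_1 to v_5 for Week 12 HAQ-DI. For mTSS make the Week 24 variable last and apply the shift to it. Treat SF-36 PCS and FACIT-Fatigue in the same way, ending at Week 12.
- Label the visit variables.

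With the target visit last, a missing target value can never be an intermittent gap, so each one is imputed with treatment and, in the shifted arms, receives the shift. The cost is a few words in two sections and a few lines of code. No new data are needed, and the primary analyses do not change.

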6.2.5. Subgroup Analysis of the Primary Endpoint

Subgroup analyses comparing each filgotinib dose group to the placebo group will be performed at Week 12 and Week 24 for the primary endpoint, for the subgroups specified in Section 3.4.

The proportion of subjects who achieve ACR20 will be analyzed using the Fisher’s exact test based on the NRI method for treatment group comparison. The number and percentage of subjects with ACR20 will also be provided for each treatment group within the subgroups.

6.3. Key Secondary Efficacy Endpoints

The key secondary efficacy endpoints are:

- Change from Baseline in HAQ-DI score at Week 12
- The proportion of subjects who achieve DAS28(CRP) < 2.6 at Week 12
- Change from Baseline in mTSS at Week 24

- The proportion of subjects who achieve $\text{DAS28(CRP)} \leq 3.2$ at Week 12
- Change from Baseline in SF-36 physical component summary (PCS) score at Week 12
- Change from Baseline in FACIT-Fatigue score at Week 12

6.3.1. Definition of Key Secondary Efficacy Endpoints

6.3.1.1. Disease Activity Score for 28 Joint Count using CRP

The DAS28(CRP) score is calculated as follows:

$$\text{DAS28(CRP)} = 0.56\sqrt{\text{TJC28}} + 0.28\sqrt{\text{SJC28}} + 0.36 \ln(\text{CRP} + 1) + 0.014 \times \text{SGA} + 0.96,$$

where

CRP = hsCRP measurement (mg/L)

SGA = subject's global assessment of disease activity on a 0-100 VAS

Higher DAS28(CRP) value indicates more severe disease activity.

No component-level imputation will be performed for the calculation of DAS28(CRP) for the primary analyses. If any components are missing, the DAS28(CRP) will be set as missing.

6.3.1.2. Modified Total Sharp Score (mTSS)

Subject's radiographs of bilateral hands, wrists and feet will be taken at screening and protocol specified visits. The radiographs will be evaluated through central review by independent joint assessors using the modified total Sharp Score (mTSS) method. The mTSS (range [0, 448]) is defined as the erosion score (range [0, 280]) plus the joint space narrowing (JSN) score (range [0, 168]). Detailed algorithm for calculating mTSS, erosion score and JSN score is described in [Appendix 3](#).

6.3.1.3. 36-Item Short-form Health Survey

The SF-36 Version 2 is a 36-item, self-reported, generic, comprehensive, and health-related quality of life questionnaire that yields an 8 health domains (physical functioning, role-physical, bodily pain, general health, vitality, social functioning, role-emotional, and mental health). Each domain is scored by summing the individual items and transforming the scores into a 0 to 100 scale with higher scores indicating better health status or functioning. In addition, 2 summary scores, the physical component summary (PCS) score and the mental component summary (MCS) score will be evaluated based on the 8 SF-36 domains.

6.3.1.4. FACIT-Fatigue

The FACIT-Fatigue scale is a brief, 13-item, symptom-specific questionnaire that specifically assesses the self-reported severity of fatigue and its impact upon daily activities and functioning in the past 7 days. The FACIT-Fatigue uses 0 (“not at all”) to 4 (“very much”) numeric rating scales. Negatively stated items are reversed by subtracting the response from “4” before being added to obtain a total score. Scores range from 0 to 52 with higher scores indicating less fatigue. In the case of missing response for some items in the questionnaire, if at least half of the items (ie, ≥ 7 of 13 items) were answered at a given visit, the prorated score will be calculated and used in the analysis.

6.3.2. Analysis Methods for Key Secondary Efficacy Endpoints

Hypothesis testing on the key secondary efficacy endpoints will commence after the testing on the primary efficacy endpoint reaches statistical significance, and will be performed according to the hierarchical testing principle at the 2-sided 0.05 level as described in Section 3.5. If a null hypothesis is not rejected, formal sequential testing will be stopped and only nominal significance will be reported for the remaining hypotheses.

For non-inferiority test of the proportion of subjects who achieve $\text{DAS28}(\text{CRP}) \leq 3.2$ at Week 12, the approach proposed by {Liu 2014} will be used to demonstrate that each filgotinib dose preserves more than 50% of the effect of adalimumab on the response rate of DAS28 (CRP) ≤ 3.2 at Week 12 using NRI. Let π_T , π_C and π_P denote the true response rates of DAS28 (CRP) ≤ 3.2 for filgotinib, adalimumab, and placebo respectively, at Week 12, with corresponding variances σ_T^2 , σ_C^2 and σ_P^2 . The non-inferiority null hypothesis is

$$H_{0,NI} : \frac{\pi_T - \pi_P}{\pi_C - \pi_P} \leq 0.5$$

According to {Liu 2014}, non-inferiority (filgotinib preserves more than 50% of the effect of adalimumab) at 2-sided 0.05 level will be claimed if $Z_{NI} > z_*$, where

$$Z_{NI} = \frac{\hat{\pi}_T - 0.5\hat{\pi}_C - (1-0.5)\hat{\pi}_P}{\sqrt{\hat{\sigma}_T^2 + 0.5^2\hat{\sigma}_C^2 + (1-0.5)^2\hat{\sigma}_P^2}}$$
 and z_* is the 97.5 quantile of the standard normal distribution.

Note that the “hat” (^) denotes the estimated values of each parameter at Week 12.

The non-inferiority test of the proportion of subjects who achieve $\text{DAS28}(\text{CRP}) < 2.6$ at Week 12 will be performed.

For the superiority test of the proportion of subjects who achieve DAS28(CRP) < 2.6 at Week 12, the similar logistic regression analysis with the same model specification as the primary endpoint analysis described in Section 6.2.3 will be adopted for the treatment comparisons. The model will include all treatment groups. The NRI method will be used to impute missing value. Comparison will be made between each filgotinib dose group and placebo group. The p-value from the logistic regression model will be reported for statistical inference. The 2-sided 95% CI of response rate based on normal approximation with the sample variance will be provided for each treatment group. In addition, non-stratified response rate difference along with its 95% CI calculated based on the normal approximation with the pooled the sample variance will be provided. The superiority test of the proportion of subjects who achieve DAS28(CRP) \leq 3.2 or DAS28(CRP) < 2.6 at Week 12 will be performed in the similar way, and the comparison will be made between each filgotinib dose group and adalimumab group.

The change from Baseline in HAQ-DI at Week 12 will be analyzed using the mixed-effects model for repeated measures (MMRM) that includes data at postbaseline visits up to the time point of interest. Subjects that have a baseline value and at least 1 postbaseline value are included in the analysis. The MMRM models will be used to evaluate treatment effect on change score from Baseline, with baseline value, stratification factors, treatment, visit, and treatment by visit interaction included as fixed effects and subject being the random effect. The MMRM model will include all treatment groups. An unstructured variance-covariance matrix will be used. The Kenward-Roger method will be used to estimate the degrees of freedom. Missing change scores due to missing study visits, early withdrawal or treatment reassignment will not be otherwise imputed using the MMRM approach. The least squares (LS) means and 95% CIs of the difference in mean change from Baseline in HAQ-DI between each filgotinib dose group and placebo group from MMRM will be provided.

The change from Baseline in mTSS, erosion score and JSN score at Week 24, and change from Baseline in SF-36 PCS score and FACIT-Fatigue score at Week 12 will be analyzed using similar MMRM method as HAQ-DI, by including data at postbaseline visits up to the time point of interest. To test for a treatment difference between each filgotinib dose group and placebo, LS mean difference along with 95% CI and p-values from the MMRM model will be presented.

The proportions of subjects achieving DAS28(CRP) \leq 3.2 (using NRI), and proportions of subjects achieving DAS28(CRP) < 2.6 (using NRI) will be plotted over time by treatment. Plots of mean \pm SD of changes from Baseline in HAQ-DI, mTSS, erosion score, JSN score, SF-36 PCS and FACIT-Fatigue over time will be presented respectively. Cumulative percentile plots will be provided for change from baseline in mTSS.

